### **Task 2. Studying the restoration of organ function during implantation of the left ventricular assist device as an organ-replacing aid in heart failure.**

Subtask 2.1. Assessment of the restoration of organ function during implantation of the left ventricular assist device with the use of extracorporeal hemocorrection.

Subtask 2.2. Assessment of the normalization of the body's immune response and restoration of organ function upon implantation of the left ventricular assist device using an extracorporeal cytokine adsorber.

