| 3                 | Inflammatory response - The level of procalcitonin [Time: 24-48 hours]

The level of procalcitonin before the start of ECMO, 2 hours after the implantation of ECMO, during ECMO, 24 hours after ECMO explantation.   |
| 4                 | Level of leukocyte [Time: 24-48 hours]

Level of leukocyte cells in the bloodstream at 24, 48 hours.  |

|                          |  |
|--------------------------|--|
| 5                 | Application and dosage of vasopressors [Deadline: first 48 hours]
Incidence of application and level of dosage of vasopressors on days 2 and 3 after surgery; |
| 6                 | Application and dosage of inotropes [Deadline: first 48 hours]
Incidence of application and level of dosage of inotropes on days 2 and 3 after surgery;       |
| Long-term results |  |
| 1                 | Length of stay in the intensive care unit [Duration: first 48 hours]   |
| 2                 | Length of hospital stay [Term: up to 1 month];   |
| 3                 | 30 day survival rate.  |

| Patients with left ventricular assist device implantation |  |
|--|--|
| Primary results   |  |
| 1   | Difference of Cytokine response [Time: 24-48 hours]
Level of pro- and anti-inflammatory cytokines (IL-1, IL-6, IL-8, IL-10, tumor necrosis factor-alfa, procalcitonin)  |
| 2   | Doses of vasopressors and / or inotropes ( $\mu$ g / h / kg bodyweight)
[Deadline: first 72 hours]  |
| 3   | Renal function [Time: first 72 hours] creatinine level   |
| 4   | Lactate level [Time: first 72 hours]   |
| Secondary results   |  |
| 1   | Inflammatory response - The level of C-reactive protein (CRP) [Time: 24-48 hours]
The level of C-reactive protein (CRP) before the start of the operation, 2 hours after the start of the operation, when the operation is turned off, 24 hours after the shutdown of the operation |
| 2   | Inflammatory response - The level of leukocytes [Time: 24-48 hours]
The level of leukocytes before the start of the operation, 2 hours after the start of the operation, when the operation is turned off, 24 hours after the shutdown of the operation                             |

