### Statistical research

- 1) statistical data processing
- 2) comparison and analysis of initial data

After data acquisition, statistical analysis will be performed using SPSS Statistics version 22. For quantitative data, the nonparametric Mann-Whitney U test and parametric t-test will be performed, and for qualitative studies, the nonparametric Fisher's exact test and the parametric  $\chi^2$  test will be performed. Also, logistic regression for categorical outcomes and survival analyzes (non-parametric Kaplan-Meyer and parametric Cox regression) will be performed.

**Age:** 18 years and older

**Gender:** All

**Inclusion of healthy volunteers:** Not

| Groups  | Inclusion criteria   | Exclusion criteria  |
|--|---|--|
| Patients on an extracorporeal life support system with heart failure                             | 
 
• Implantation of intravenous ECMO
 
• Hemodynamic support with vasopressors and / or tonics;
 
• Procalcitonin level <math>\geq 1</math> ng / ml;
 
• Invasive hemodynamic monitoring;
 
• Written informed consent.
 
   | 
 
• Age less than 18 years old
 
• Terminal hepatic or renal failure just before the procedure
 
• Patient's written refusal to participate in the study
 
 |
| Patients on an extracorporeal life support system with pulmonary failure                         | 
 
• IV ECMO implantation
 
• High levels of venous and arterial CO2 (CO2 > 50 mmHg),
 
• Low paO2, SvO2, SpO2.
 
• Invasive hemodynamic monitoring;
 
• Written informed consent.
 
                                     | 
 
• Age less than 18 years old
 
• Terminal hepatic or renal failure just before the procedure
 
• Patient's written refusal to participate in the study
 
 |

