| Patients with left ventricular assistive device implantation                                     | 
 
• LVAD implantation
 
• Biventricular heart failure IV
 
• INTERMACS I-III
 
• Hemodynamic support with vasopressors and / or tonics;
 
• Procalcitonin level <math>\geq 0.1</math> ng / ml;
 
• Invasive hemodynamic monitoring;
 
• Written informed consent.
 
 | 
 
• Age less than 18 years old
 
• Acute hepatic or renal failure just before the procedure
 
• Patient's written refusal to participate in the study
 
    |
| Patients in operations with prolonged artificial circulation, hypothermia and circulatory arrest | 
 
• Hemodynamic support with vasopressors and / or tonics;
 
• Bypass duration > 120 minutes
 
• Hypothermia <math>\leq 25</math> 0C
 
• Circulatory arrest
 
   | 
 
• Age less than 18 years old
 
• Terminal hepatic or renal failure just before the procedure
 
• Patient's written refusal to
 
                          |

|  |   |                          |
|--|---|--------------------------|
|  | 
 
• Procalcitonin level <math>\geq 1</math> ng / ml;
 
• Invasive hemodynamic monitoring;
 
• Written informed consent.
 
 | participate in the study |
|--|---|--------------------------|

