| 4.7 | Collection of laboratory and clinical data, blood sampling for pro- and anti-inflammatory cytokines, assessment of organ dysfunction, dose of vasopressors after implantation of an auxiliary device of the left ventricle and implantation of a completely artificial heart as an organ-replacing aid in case of heart failure. | 2021 | 36 | There will be a collection laboratory and clinical data, blood sampling for pro- and anti-inflammatory cytokines, assessment of organ dysfunction, dose of vasopressors after implantation of an auxiliary device of the left ventricle and implantation of a completely artificial heart as an organ-replacing aid in case of heart failure | There will be a collection laboratory and clinical data, blood sampling for pro- and anti-inflammatory cytokines, assessment of organ dysfunction, dose of vasopressors after implantation of an auxiliary device of the left ventricle and implantation of a completely artificial heart as an organ-replacing aid in case of heart failure | There will be a collection laboratory and clinical data, blood sampling for pro- and anti-inflammatory cytokines, assessment of organ dysfunction, dose of vasopressors after implantation of an auxiliary device of the left ventricle and implantation of a completely artificial heart as an organ-replacing aid in case of heart failure |
| 4.8 | Data collection of inflammatory response, leukocyte function, inotropic support doses after implantation of an   | 2021 | 36 | There will be a collection inflammatory response data, leukocyte function, inotropic support doses after implantation of an auxiliary  | There will be a collection inflammatory response data, leukocyte function, inotropic support doses after implantation of an auxiliary  | There will be a collection inflammatory response data, leukocyte function, inotropic support doses after implantation of an auxiliary  |

|      |   |      |    |  |  |  |
|------|---|------|----|--|--|--|

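### The LVAD eligibility row excludes acute instead of terminal hepatic or renal failure, without explanation, and the LVAD creatinine primary has no rule for renal replacement therapy or death

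*Combined protocol and SAP*

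**What the plan says.** The eligibility table under Statistical research has four rows. Both extracorporeal life support rows and the prolonged-bypass row exclude "Terminal hepatic or renal failure just before the procedure". The LVAD row instead excludes "Acute hepatic or renal failure just before the procedure". The document defines neither acute nor terminal failure and does not explain the difference.

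Task 2, in the program objectives, is "Studying the restoration of organ function during implantation of the left ventricular assist device". Subtask 2.2 adds normalization of the immune response.

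Performance evaluation criterias lists four LVAD primary results:

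- row 1: "Difference of Cytokine response [Time: 24-48 hours"
- row 2: "Doses of vasopressors and / or inotropes", over 72 hours
- row 3: "Renal function [Time: first 72 hours] creatinine level"
- row 4: "Lactate level [Time: first 72 hours"

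Row 3 does not mention renal replacement therapy or death. Days on replacement therapy are counted only in the ECMO table (primary row 6). Research methods and ethical issues puts 5 LVAD patients in each arm, and Study design states that there is no masking. Statistical research plans both the Mann-Whitney test and the t-test for quantitative data, without saying which governs.

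**The concern.** There are two linked problems.

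The first is who enters. Taken as written, the LVAD row turns away a patient with overt acute kidney or liver failure, which may be reversible. It does not turn away a patient with terminal renal failure, whose creatinine reflects that failure or the therapy replacing the kidney. The other rows do the opposite. The mismatch falls on the only outcome table that lists creatinine as a result of its own.

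The second is how creatinine is read after randomization. Replacement therapy lowers it, so a patient whose kidneys have failed can show a better value than one who was never treated. A patient who dies has no later value. Both events occur after allocation and can differ by arm, and replacement therapy is started by staff who know the device. An arm could therefore look better on this primary because more of its patients were dialysed or died.

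**Working it through.** **Eligibility rows side by side**

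| Row | Acute failure excluded? | Terminal failure excluded? |
|---|---|---|
| Life support, heart failure | not mentioned | yes |
| Life support, pulmonary failure | not mentioned | yes |
| LVAD | yes | not mentioned |
| Prolonged bypass | not mentioned | yes |

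One row of four differs. It governs 5 × 2 = 10 of the 100 patients. The subgroup sizes agree with the total: 10 + 10 + 5 + 25 = 50 per arm, and 50 × 2 = 100.

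**Which LVAD primaries are touched.** Cytokines, vasopressor or inotrope dose, and lactate do not need renal or hepatic failure at entry to be informative. Creatinine, one of the four, is the result affected. The LVAD table contains no hepatic measure.

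**Illustration of the creatinine problem.** The plan gives no creatinine values, so all inputs here are assumed (µmol/L).

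- Arm X: three patients at 120, and two in kidney failure at 300 who start replacement therapy and then read r, taken first as 150.
- Arm Y: four patients at 120, and one at 200 without replacement therapy.

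Means:

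- X as measured: (3 × 120 + 2 × 150) / 5 = 660 / 5 = 132
- Y: (4 × 120 + 200) / 5 = 680 / 5 = 136
- X had replacement therapy not lowered the values: (3 × 120 + 2 × 300) / 5 = 960 / 5 = 192

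X has two failures but the lower mean. This reversal needs (360 + 2r) / 5 < 136, that is r < 160.

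Raw ranks at r = 150 (higher is worse): the seven values of 120 share rank 4, the two of 150 share 8.5, and 200 takes rank 10.

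- X: 3 × 4 + 2 × 8.5 = 29
- Y: 4 × 4 + 10 = 26

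The Mann-Whitney comparison does not reverse at this value, but it still places both replaced patients ahead of the untreated patient at 200. It would reverse if replacement therapy brought the reading down to 120. Nine values would then share rank 5, giving X 5 × 5 = 25 and Y 4 × 5 + 10 = 30.

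With the two replaced patients ranked worst, they share rank 9.5 and 200 takes rank 8.

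- X: 3 × 4 + 2 × 9.5 = 31
- Y: 4 × 4 + 8 = 24

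These sums do not depend on r. Two patients move the rank-sum gap from 29 − 26 = 3 to 31 − 24 = 7.

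**The case against.** The strongest reply is that this is a wording slip with little consequence. The text reads as translated, and acute may be either an error or a deliberate choice. The documents do not settle which. That stands, and it is why the point asks for reconciliation and does not allege a harmful design.

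A reader might infer that Task 2 cannot be answered, or that the LVAD group can show at best preservation of function. The documents do not support either. Task 2 covers organ function generally and, through Subtask 2.2, the immune response. Three of the four primaries do not depend on renal failure at entry. Dysfunction short of failure remains eligible. Patients enter at INTERMACS I-III on vasopressors and/or inotropes, so circulatory recovery can be observed, as can recovery from failure that arises on study.

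A reader might also infer bias between the devices from the exclusion. It applies to both randomized arms, so it affects generalizability and the range of creatinine change, not the contrast. This reply does not cover replacement therapy or death after randomization.

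On the illustration, the objection is right that at a reading of 150 only the means reverse. The plan gives no expected rate of replacement therapy in LVAD patients, and the ECMO table's count cannot supply one.

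Finally, 5 per arm limits any comparison. Assuming two-sided alpha 0.05, t-test power is about 11%, 20% and 29% for differences of 0.5, 0.8 and 1.0 SD. That stands under either wording. It does not excuse an outcome that can rank patients in the wrong order.

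**Conclusion.** The concern holds in a limited form. The LVAD exclusion contradicts the other three rows without reason or definition. As written, it leaves renal and hepatic recovery only weakly assessable in 10 of 100 patients, through one of four primaries.

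Separately, raw creatinine with no rule for replacement therapy or death can misorder patients, and with 5 per arm one or two of them can change the result. How often this would happen cannot be derived from the documents. The 132 against 136 example shows the mechanism under assumed values and is not an estimate. Its reversal of the means needs a reading under replacement therapy below 160.

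**What to change.** 1. Reconcile the organ-failure exclusions across the four rows, define acute and terminal, and give the reason if the difference is intended. This review does not say which exclusion is right. Match the wording of Task 2 and Subtasks 2.1 and 2.2 to what is kept.

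2. Record the start of renal replacement therapy in LVAD patients. In LVAD primary row 3, rank any patient who starts it or dies within 72 hours as worse than every measured creatinine, and compare the arms with the Mann-Whitney test already planned. The row gives a window but no sampling time, so name the time at which creatinine is ranked. If the reconciled wording leaves patients already on replacement therapy eligible, say how they are ranked.

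3. Optional: SOFA as a secondary LVAD result only, if its components are recorded. Work-plan row 4.7 foresees "assessment of organ dysfunction, dose of vasopressors after implantation of an auxiliary device of the left ventricle" but does not name SOFA.

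The cost is protocol wording and one recorded item. Perioperative complications and survival are already to be documented, but replacement therapy is not listed for LVAD patients, so its recording must be confirmed. A ranked outcome is also less direct to describe than a mean. Mean creatinine can still be reported descriptively beside the counts of replacement therapy and death.

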## 8. Plan for the implementation of the program.

| P /
p
No. | Name of tasks and
measures for their
implementation   | Start of
execution
(dd / mm /
yy) | Duration,
months | Expected results of the program implementation (in the context of tasks and activities),
completion form  |          |          |
|-----------------|---|--|---------------------|--|----------|----------|
|                 |   |  |                     | 1st year   | 2nd year | 3rd year |
| 1               | 2   | 4  | 5                   | 6  | 7        | 8        |
| 1               | Literature review on
organ replacement
technology in the
treatment of patients with
heart and pulmonary
insufficiency  | 2021                                       | 9                   | A literature review on organ
replacement technology in
the treatment of patients with
heart and lung failure will be
obtained.   |          |          |
| 1.1             | A review of the literature
on the restoration of
organ function when
using extracorporeal life
support systems as an
organ-substituting aid for
heart and pulmonary | 2021                                       | 3                   | A review of the literature on
the restoration of organ
function using extracorporeal
life support systems as an
organ-substituting aid for
heart and pulmonary failure
will be obtained. |          |          |

|     |   |      |   |  |  |  |
|-----|---|------|---|--|--|--|
|     | failure.  |      |   |  |  |  |
| 1.2 | Literature review on implantation of mechanical circulatory devices using an extracorporeal cytokine adsorber   | 2021 | 3 | A literature review on the implantation of mechanical circulatory devices using an extracorporeal cytokine adsorber will be obtained.  |  |  |
| 1.3 | Literature review on the use of an extracorporeal cytokine adsorber in operations with prolonged artificial circulation, hypothermia and circulatory arrest | 2021 | 3 | A literature review will be obtained on the use of an extracorporeal cytokine adsorber in operations for reconstructing the aortic arch with hypothermia and cardiopulmonary bypass. |  |  |
| 2   | Based on the literature review, conduct a comparative assessment of the application of methods of extracorporeal hemoadsorption in                          | 2021 | 9 | Comparative evaluation will be carried out on the application of methods of extracorporeal hemoadsorption in pulmonary and heart failure   |  |  |

|     |  |      |    |  |   |   |
|-----|--|------|----|--|---|---|
|     | pulmonary and heart failure  |      |    |  |   |   |
| 3   | Patient recruitment  | 2021 |    | Patient recruitment for the study will begin   | Patient recruitment will continue   | Patient recruitment will continue   |
| 3.1 | Recruiting of patients using extracorporeal life support systems as an organ-substituting aid for heart and pulmonary failure. | 2021 | 36 | Recruiting of patients using extracorporeal life support systems as an organ-substituting aid for heart and pulmonary failure. | Recruiting of patients when using extracorporeal life support systems, as an organ-substituting aid, with heart and pulmonary failure will continue | Recruiting of patients when using extracorporeal life support systems, as an organ-substituting aid, with heart and pulmonary failure will continue |
| 3.2 | Recruiting of patients for implantation of mechanical circulatory devices using an extracorporeal cytokine adsorber            | 2021 | 36 | Recruiting will begin patients with implantation of mechanical circulatory devices using an extracorporeal cytokine adsorber   | Recruiting patients for implantation of mechanical circulatory devices using an extracorporeal cytokine adsorber will continue                      | Recruiting patients for implantation of mechanical circulatory devices using an extracorporeal cytokine adsorber will continue                      |
| 3.3 | Recruiting of patients for hypothermia and cardiopulmonary bypass reconstruction with an extracorporeal cytokine               | 2021 | 36 | Will be started recruiting of patients for reconstructions of the aortic arch with hypothermia and cardiopulmonary bypass      | Recruiting of patients for hypothermia and cardiopulmonary bypass reconstruction with an extracorporeal cytokine                                    | Recruiting of patients for hypothermia and cardiopulmonary bypass reconstruction with an extracorporeal cytokine                                    |

|     | adsorber  |      |    | using an extracorporeal cytokine adsorber  | adsorber will continue   | adsorber will continue   |
|-----|---|------|----|--|--|--|
| 4   | Collection of laboratory and clinical data  | 2021 | 36 | There will be a collection laboratory and clinical data  | There will be a collection laboratory and clinical data  | There will be a collection laboratory and clinical data  |
| 4.1 | Collection of laboratory and clinical data, blood sampling for pro- and anti-inflammatory cytokines, assessment of organ dysfunction, dose of vasopressors after implantation of extracorporeal life support systems as an organ-substituting aid for pulmonary failure | 2021 | 36 | There will be a collection laboratory and clinical data, blood sampling for pro- and anti-inflammatory cytokines, assessment of organ dysfunction, dose of vasopressors after implantation of extracorporeal life support systems as an organ-substituting aid for pulmonary failure | There will be a collection laboratory and clinical data, blood sampling for pro- and anti-inflammatory cytokines, assessment of organ dysfunction, dose of vasopressors after implantation of extracorporeal life support systems as an organ-substituting aid for pulmonary failure | There will be a collection laboratory and clinical data, blood sampling for pro- and anti-inflammatory cytokines, assessment of organ dysfunction, dose of vasopressors after implantation of extracorporeal life support systems as an organ-substituting aid for pulmonary failure |
| 4.2 | Collection of data on the inflammatory response, leukocyte function, doses of inotropic support after implantation of   | 2021 | 36 | There will be a collection data on inflammatory response, leukocyte function, doses of inotropic support after implantation of   | There will be a collection data on inflammatory response, leukocyte function, doses of inotropic support after implantation of   | There will be a collection data on inflammatory response, leukocyte function, doses of inotropic support after implantation of   |

|     |   |      |    |  |  |  |
|-----|---|------|----|--|--|--|
|     | extracorporeal life support systems as an organ-substituting aid for pulmonary failure  |      |    | extracorporeal life support systems as an organ-substituting aid for pulmonary failure   | extracorporeal life support systems as an organ-substituting aid for pulmonary failure   | life support systems as an organ-substituting aid for pulmonary failure  |
| 4.3 | Long-term results collection: length of stay in the intensive care unit, 30 day survival after implantation of extracorporeal life support systems as an organ-substituting aid for pulmonary failure | 2021 | 36 | Long-term results will be collected: length of stay in the intensive care unit, 30 day survival after implantation of extracorporeal life support systems as an organ-substituting aid for pulmonary failure | Long-term results will be collected: length of stay in the intensive care unit, 30 day survival after implantation of extracorporeal life support systems as an organ-substituting aid for pulmonary failure | Long-term results will be collected: length of stay in the intensive care unit, 30 day survival after implantation of extracorporeal life support systems as an organ-substituting aid for pulmonary failure |
| 4.4 | Collection of laboratory and clinical data, blood sampling for pro- and anti-inflammatory cytokines, assessment of organ dysfunction, dose of vasopressors after                                      | 2021 | 36 | There will be a collection laboratory and clinical data, blood sampling for pro- and anti-inflammatory cytokines, assessment of organ dysfunction, doses of vasopressors after                               | There will be a collection laboratory and clinical data, blood sampling for pro- and anti-inflammatory cytokines, assessment of organ dysfunction, doses of vasopressors after                               | There will be a collection laboratory and clinical data, blood sampling for pro- and anti-inflammatory cytokines, assessment of organ dysfunction, doses of vasopressors after                               |

|     | implantation of extracorporeal life support systems as an organ-substituting aid in heart failure   |      |    | implantation of extracorporeal life support systems as an organ-substituting aid in heart failure   | implantation of extracorporeal life support systems as an organ-substituting aid in heart failure   | implantation of extracorporeal life support systems as an organ-substituting aid in heart failure   |
|-----|---|------|----|---|---|---|
| 4.5 | Collection of data on inflammatory response, leukocyte function, doses of inotropic support after implantation of extracorporeal life support systems as an organ-substituting aid in heart failure | 2021 | 36 | There will be a collection data on inflammatory response, leukocyte function, doses of inotropic support after implantation of extracorporeal life support systems as organ-substituting benefits for heart failure | There will be a collection data on inflammatory response, leukocyte function, doses of inotropic support after implantation of extracorporeal life support systems as organ-substituting benefits for heart failure | There will be a collection data on inflammatory response, leukocyte function, doses of inotropic support after implantation of extracorporeal life support systems as organ-substituting benefits for heart failure |
| 4.6 | Long-term results collection: length of stay in the intensive care unit, 30 day survival after implantation of extracorporeal life support systems as an  | 2021 | 36 | There will be a collection long-term results: length of stay in the intensive care unit, 30 day survival after implantation of extracorporeal life support systems as an organ-                                     | There will be a collection long-term results: length of stay in the intensive care unit, 30 day survival after implantation of extracorporeal life support systems as an organ-                                     | There will be a collection long-term results: length of stay in the intensive care unit, 30 day survival after implantation of extracorporeal life support systems as an organ-substituting aid for                 |

|     | organ-substituting aid for heart failure   |      |    | substituting aid for heart failure   | substituting aid for heart failure   | heart failure  |
|-----|--|------|----|--|--|--|
| 4.7 | Collection of laboratory and clinical data, blood sampling for pro- and anti-inflammatory cytokines, assessment of organ dysfunction, dose of vasopressors after implantation of an auxiliary device of the left ventricle and implantation of a completely artificial heart as an organ-replacing aid in case of heart failure. | 2021 | 36 | There will be a collection laboratory and clinical data, blood sampling for pro- and anti-inflammatory cytokines, assessment of organ dysfunction, dose of vasopressors after implantation of an auxiliary device of the left ventricle and implantation of a completely artificial heart as an organ-replacing aid in case of heart failure | There will be a collection laboratory and clinical data, blood sampling for pro- and anti-inflammatory cytokines, assessment of organ dysfunction, dose of vasopressors after implantation of an auxiliary device of the left ventricle and implantation of a completely artificial heart as an organ-replacing aid in case of heart failure | There will be a collection laboratory and clinical data, blood sampling for pro- and anti-inflammatory cytokines, assessment of organ dysfunction, dose of vasopressors after implantation of an auxiliary device of the left ventricle and implantation of a completely artificial heart as an organ-replacing aid in case of heart failure |
| 4.8 | Data collection of inflammatory response, leukocyte function, inotropic support doses after implantation of an   | 2021 | 36 | There will be a collection inflammatory response data, leukocyte function, inotropic support doses after implantation of an auxiliary  | There will be a collection inflammatory response data, leukocyte function, inotropic support doses after implantation of an auxiliary  | There will be a collection inflammatory response data, leukocyte function, inotropic support doses after implantation of an auxiliary  |

|      |   |      |    |  |  |  |
|------|---|------|----|--|--|--|
|      | auxiliary device of the left ventricle and implantation of a completely artificial heart as an organ-replacing aid in case of heart failure.  |      |    | device of the left ventricle and implantation of a completely artificial heart as an organ-replacing aid in case of heart failure.   | device of the left ventricle and implantation of a completely artificial heart as an organ-replacing aid in case of heart failure.   | device of the left ventricle and implantation of a completely artificial heart as an organ-replacing aid in case of heart failure.   |
| 4.9  | Long-term data collection: length of stay in the intensive care unit, 30 day survival after implantation of an auxiliary device of the left ventricle and implantation of a completely artificial heart as an organ-replacing aid in case of heart failure. | 2021 | 36 | There will be a collection long-term results: length of stay in the intensive care unit, 30 day survival after implantation of an auxiliary device of the left ventricle and implantation of a completely artificial heart as an organ-replacing aid in case of heart failure. | There will be a collection long-term results: length of stay in the intensive care unit, 30 day survival after implantation of an auxiliary device of the left ventricle and implantation of a completely artificial heart as an organ-replacing aid in case of heart failure. | There will be a collection long-term results: length of stay in the intensive care unit, 30 day survival after implantation of an auxiliary device of the left ventricle and implantation of a completely artificial heart as an organ-replacing aid in case of heart failure. |
| 4.10 | Collection of laboratory and clinical data, blood sampling for pro- and anti-inflammatory   | 2021 | 36 | There will be a collection laboratory and clinical data, blood sampling for pro- and anti-inflammatory cytokines,  | There will be a collection laboratory and clinical data, blood sampling for pro- and anti-inflammatory cytokines,  | There will be a collection laboratory and clinical data, blood sampling for pro- and anti-inflammatory cytokines,  |

|      |  |      |    |   |   |   |
|------|--|------|----|---|---|---|
|      | cytokines, assessment of organ dysfunction, dose of vasopressors during operations with prolonged artificial circulation, hypothermia and circulatory arrest, as an organ-substituting aid                         |      |    | assessment of organ dysfunction, dose of vasopressors after reconstruction of the aortic arch with long-term artificial circulation and hypothermia, as an organ-replacing aid  | assessment of organ dysfunction, dose of vasopressors after reconstruction of the aortic arch with long-term artificial circulation and hypothermia, as an organ-replacing aid  | assessment of organ dysfunction, dose of vasopressors after reconstruction of the aortic arch with long-term artificial circulation and hypothermia, as an organ-replacing aid  |
| 4.11 | Collection of data on inflammatory response, leukocyte function, inotropic support doses during operations with prolonged artificial circulation, hypothermia and circulatory arrest, as an organ-substituting aid | 2021 | 36 | There will be a collection inflammatory response data, leukocyte function, inotropic support doses after reconstruction of the aortic arch with long-term artificial circulation and hypothermia, as an organ-replacing aid | There will be a collection inflammatory response data, leukocyte function, inotropic support doses after reconstruction of the aortic arch with long-term artificial circulation and hypothermia, as an organ-replacing aid | There will be a collection inflammatory response data, leukocyte function, inotropic support doses after reconstruction of the aortic arch with long-term artificial circulation and hypothermia, as an organ-replacing aid |
| 4.12 | Long-term data collection: length of stay in the intensive care unit, 30 day survival after  | 2021 | 36 | There will be a collection long-term results: length of stay in the intensive care unit, 30 day survival after  | There will be a collection long-term results: length of stay in the intensive care unit, 30 day survival after  | There will be a collection long-term results: length of stay in the intensive care unit, 30 day survival after  |

|   |  |      |    |  |  |  |
|---|--|------|----|--|--|--|
|   | operations with long-term artificial circulation, hypothermia and circulatory arrest, as an organ-substituting aid |      |    | reconstruction of the aortic arch with long-term artificial circulation and hypothermia, as an organ-replacing aid | reconstruction of the aortic arch with long-term artificial circulation and hypothermia, as an organ-replacing aid                 | reconstruction of the aortic arch with long-term artificial circulation and hypothermia, as an organ-replacing aid                 |
| 5 | Analysis of clinical and laboratory data on the restoration of organ function using innovative technologies        | 2022 | 24 |  | An analysis of clinical and laboratory data on the restoration of organ function will be carried out using innovative technologies | An analysis of clinical and laboratory data on the restoration of organ function will be carried out using innovative technologies |
| 6 | Statistical processing and analysis of the obtained data   | 2022 | 24 |  | Statistical processing of the obtained research results will be carried out  | Statistical processing of the obtained research results will be carried out  |
| 7 | Determination of an effective method of treating heart and pulmonary failure using organ replacement technologies. | 2023 | 12 |  |  | An effective method will be determined of the treatment of heart and pulmonary failure using organ replacement technologies        |
| 8 | Development of innovative methods of   | 2022 | 24 |  | Innovative methods of treating patients using  | Innovative methods of treating patients using organ-   |

|    |  |      |    |                                 |   |   |
|----|--|------|----|---------------------------------|---|---|
|    | treating patients using organ-replacing technologies                             |      |    |                                 | organ-replacing technologies will be developed                  | replacing technologies will be developed  |
| 9  | Development of practical protocols for the restoration of organ function         | 2022 | 24 |                                 | Practical protocols to restore organ function will be developed | Practical protocols to restore organ function will be developed                   |
| 10 | Implementation of patient treatment protocols using organ-replacing technologies | 2023 | 12 |                                 |   | Patient treatment protocols using organ-replacing technologies will be introduced |
| 11 | Writing and submission of interim and final reports                              | 2021 | 36 | Interim report will be prepared | Interim report will be prepared                                 | Final report will be prepared   |
| 12 | Preparation of publications, reports   | 2022 | 24 |                                 | Publications will be prepared                                   | Publications will be prepared   |

